7.1.2 Liver Chemistry Stopping Criteria

Discontinuation of blinded study medication for abnormal liver function should be considered by the Investigator when a patient meets one of the conditions outlined in Section 11.9 or if the Investigator believes that it is in best interest of the patient.

7.1.3 Electrocardiogram Withdrawal Criteria

All ECGs conducted or overread after a patient has been randomized will be subject to ECG Withdrawal Criteria (Section 11.5). Patients may be discontinued from blinded study medication if they experience a significant abnormality(ies) on their ECG including, but not limited to those listed in the ECG Withdrawal Criteria, Section 11.5 and in consideration with the patient’s medical history and baseline ECG measurements. Clinically significant abnormalities as determined by the Investigator may also result in patient discontinuation from study medication per the Investigator’s judgement. Triplicate ECGs (over a brief period of time) should be performed on patients experiencing a

significant abnormality on their ECG or other clinically significant abnormality as determined by the Investigator. The intent of triplicate ECG measurements is to differentiate significant abnormalities from artifact. Abnormalities should be confirmed in 2 of 3 triplicate ECG measurements.

7.1.4 COPD Exacerbation Withdrawal Criteria

Guidelines for identifying COPD exacerbation in this study and conditions for study continuation or withdrawal due to COPD exacerbation can be found in Section 11.6.

7.1.5 Positive Pregnancy Test in Females

Women who are pregnant or breastfeeding are not eligible to participate. Pregnancy testing is being conducted in women of childbearing potential at Screening and at other times specified in the SoA (Section 1.3).

Women exhibiting a positive pregnancy test (Section 11.3) during the study will be discontinued from blinded study medication and followed-up per the Collection of Pregnancy Information guidelines in Section 8.7.5 and Section 11.8.

7.1.6 Positive COVID-19 Test Indicating an Active Infection

Patients with a positive COVID-19 test result indicating an active infection will be required to discontinue blinded study medication and will be required to withdraw from the study.

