7.0 DISCONTINUATION OF BLINDED STUDY MEDICATION AND PATIENT DISCONTINUATION/WITHDRAWAL

7.1 Discontinuation of Blinded Study Medication

Patients who permanently discontinue blinded study medication are not required to withdraw from the study unless they test positive for COVID-19 active disease. If a patient must permanently discontinue blinded study medication for reason(s) other than testing positive for COVID-19 active disease, the patient should complete the “Patient Discontinuation/Withdrawal from the Study” assessments described in Section 7.3 as soon as possible. In addition, every effort should be made by the investigator/staff to keep the patient in the study to collect important efficacy and safety data as detailed in Section 7.2.

Circumstances potentially requiring or actually resulting in discontinuation of blinded study medication are described below.

See the SoA (Section 1.3) for data to be collected at the time of treatment discontinuation and follow-up and for any further evaluations that need to be completed.

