7.2 Study Participation After Discontinuation of Blinded Study Medication

Patients may permanently discontinue blinded study medication before the end of the study if they choose to or at the investigator's discretion.

Patients who permanently discontinue blinded study medication are not required to withdraw from the study unless they test positive for COVID-19 active disease. Patients who have permanently discontinued blinded study medication but do not test positive for COVID-19 active disease and have not withdrawn consent may continue in the study and complete all remaining protocol specified visits.

The Investigator must document the reason for discontinuation of blinded study medication in the eCRF.

Ideally, patients who have permanently discontinued blinded study medication will continue to attend scheduled clinic visits and complete important efficacy and safety assessments. However, if this is not possible then the investigator will encourage the patient to select one of the three options below to participate in as much of the study as they are willing (or able) to participate:

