7.2.1 Reduced Assessments

The patient continues to follow the SoA (Section 1.3) and completes only the following assessments:

- Spirometry
- SGRQ
- COPD exacerbation
- AE
- Concomitant medication

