7.2.3 Phone Contact Only

The site contacts the patient by phone per the SoA (Section 1.3) to complete the following assessments:

- COPD exacerbation
- SAE
- Concomitant medication

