8.4.3.1 COVID-19

Testing for COVID-19 may optionally be completed (Section 11.3). Patients with a positive COVID-19 test result indicating an active infection anytime during the study will be withdrawn.

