11.6.7 Study Continuation or Withdrawal Due to COPD Exacerbation

- Patients who experience a single COPD exacerbation during the treatment period may remain in the study and should continue to take their blinded study medication if possible and record their symptoms and rescue albuterol/salbutamol usage in their eDiary.
- Patients who experience a second COPD exacerbation and/or a severe COPD exacerbation that requires in-patient hospitalization will be discontinued from study treatment (Section 7.0).

11.7 Appendix 7: Adverse Events: Definitions and Procedures for Recording, Evaluating, Follow-up and Reporting

Definition of AE

- An AE is any untoward medical occurrence in a patient or subject, temporally associated with the use of blinded study medication, whether or not considered related to the blinded study medication.
- NOTE: An AE can therefore be any unfavorable and unintended sign (including an abnormal laboratory finding), symptom, or disease (new or exacerbated) temporally associated with the use of blinded study medication.

Events Meeting the AE Definition

- Any abnormal laboratory test results (eg, hematology, clinical chemistry) or other safety assessments (eg, ECG, radiological scans, vital signs measurements), including those that worsen from baseline, considered clinically significant in the medical and scientific judgment of the Investigator (ie, not related to progression of underlying disease).
- Exacerbation of a chronic or intermittent pre-existing condition including either an increase in frequency and/or intensity of the condition.
- New conditions detected or diagnosed after blinded study medication administration even though it may have been present before the start of the study.
- Signs, symptoms, or the clinical sequelae of a suspected drug-drug interaction.
- Signs, symptoms, or the clinical sequelae of a suspected overdose of either blinded study medication or a concomitant medication. Overdose per se will not be reported as an AE/SAE unless it is an intentional overdose taken with possible suicidal/self-harming intent. Such overdoses should be reported regardless of sequelae.
- “Lack of efficacy” or “failure of expected pharmacological action” per se will not be reported as an AE or SAE. Such instances will be captured in the efficacy assessments. However, the signs, symptoms and/or clinical sequelae resulting from lack of efficacy will be reported as an AE or SAE if they fulfil the definition of an AE or SAE.

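### Active COVID-19 forces patients out of the study as well as off drug, so later outcomes that the treatment-policy estimands call for are not collected

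*Protocol*

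**What the plan says.** The rule appears in four places in the Protocol. Section 7.1.6 says that patients with a test showing active infection "will be required to discontinue blinded study medication and will be required to withdraw from the study". Section 7.1 says that patients who stop drug are "not required to withdraw from the study unless they test positive for COVID-19 active disease", and Section 7.2 repeats this. Section 8.4.3.1 adds: "Patients with a positive COVID-19 test result indicating an active infection anytime during the study will be withdrawn".

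Other patients who stop drug and "have not withdrawn consent may continue in the study and complete all remaining protocol specified visits". If full visits are not possible, Section 7.2 offers three lighter options:

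- **7.2.1:** scheduled visits limited to spirometry, SGRQ, exacerbations, AEs and concomitant medication.
- **7.2.2:** phone contact, plus a clinic return at Week 24 (and Week 48 in that stratum) that includes spirometry and SGRQ.
- **7.2.3:** phone contact alone, for exacerbations, SAEs and concomitant medication.

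Even a patient with a "severe COPD exacerbation that requires in-patient hospitalization will be discontinued from study treatment" only (11.6.7), with no exit from the study. Pregnancy (11.8) is the one other event for which the Protocol requires study exit.

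On the analysis side, SAP Table 1 applies treatment policy to the lung-function, E-RS and SGRQ estimands. SAP 7.3 uses off-treatment data and end-of-study visits. What is still missing goes to multiple imputation under MAR (16.1.2, 16.2.2.1). For non-completers, exacerbation time ends at the end-of-study date (16.3.3).

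**The concern.** A treatment-policy estimand needs outcomes after the drug stop. For COVID-19 the Protocol itself ends their collection, although Section 7.2 already provides the means to obtain them. A patient who has recovered could attend for Week 24 spirometry and SGRQ. While infectious, the patient could report exacerbations and SAEs by phone, and Protocol 8.6.2.3 already allows phone or video contact when a clinic visit is impossible.

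Three things are at stake:

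- Spirometry and SGRQ values at Weeks 12 and 24 are replaced by a single exit value or by MAR imputation.
- Exacerbation follow-up is censored by a respiratory illness, so the censoring may be informative.
- SAE collection stops at the follow-up contact 4 to 10 days after the early-termination visit (4.1, 8.7.1).

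The two clarification letters described in SAP 17.5 tie active infection first to symptoms and then to lower respiratory symptoms. That reduces the number affected, but it concentrates the loss in patients whose respiratory outcomes matter most. COVID-19 disruption is recorded (Protocol 8.6.3.3, SAP 17.5), yet no sensitivity analysis addresses these withdrawals.

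**Working it through.** **The plan's own figure.** Inputs from Protocol 9.2: SD 250 mL, difference 59 mL, 500 v 300 evaluable, two-sided 5%, stated power 90%.

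- SE = 250 × √(1/500 + 1/300) = 18.26 mL.
- Power = Φ(59/18.26 − 1.96) = Φ(1.27) = 89.8%, which agrees with the stated 90%.

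**Assumed exits.** The documents give no COVID-19 rate, and testing is optional. I assume that 2%, 5% or 10% of 800 exit within 24 weeks, evenly over time and in equal shares by arm. On their own, all three stay below the 25% withdrawal rate at which patients may be added (9.2).

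**Formulas.**

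- Power with a fraction p lost and none recovered: Φ(3.23 × √(1 − p) − 1.96).
- Upper bound on primary bias: p × 59 mL. This supposes that every exit falls before Week 12, that no early-termination data exist, that the off-drug effect is zero, and that imputation carries the full effect forward.
- Exacerbation time lost to Week 24: patients × 12/52, out of 800 × 24/52 = 369.2 patient-years. This share is c = 1.0%, 2.5% or 5.0%.
- Exacerbation illustration, with an assumed rate ratio of 0.70 and the lost time filled at the placebo rate in both arms: (1 − c) × 0.70 + c.

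| Assumed exits | Patients | Power, half before Week 12 | Power, all before Week 12 | Bias bound (mL) | Patient-years lost | 0.70 becomes |
|---|---|---|---|---|---|---|
| 2% | 16 | 89.5% | 89.2% | 1.2 | 3.7 | 0.703 |
| 5% | 40 | 89.1% | 88.3% | 3.0 | 9.2 | 0.708 |
| 10% | 80 | 88.3% | 86.6% | 5.9 | 18.5 | 0.715 |

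If 25% to 75% of these patients stayed (also an assumption), the recovered exacerbation time would be 0.9–2.8, 2.3–6.9 or 4.6–13.8 patient-years. These figures fit only the analysis truncated at Week 24. Exits in Weeks 25–48 would add to the loss in the other two exacerbation analyses of SAP 16.3.3.

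**The early-termination visit.** Protocol 4.1 requests these procedures from any patient meeting withdrawal criteria, and 7.3.1 presses for them before Week 12. Section 7.1, however, limits its instruction to patients who stop "for reason(s) other than testing positive for COVID-19 active disease, the patient should complete the" withdrawal assessments. Section 7.3.1.1 makes the serial spirometry optional for patients already off drug, as these patients must be. Where the visit takes place, SAP 6.4 uses its 12-hour spirometry whatever its timing and maps its questionnaires to a scheduled visit. It still gives one value near the acute infection, not a later outcome.

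**Sensitivity analyses for patients already withdrawn.** SAP 16.2.2.4 extends the tipping point to key secondary endpoints, and SAP 7.4 tests E-RS and SGRQ at Week 24. The lead-in to SAP 16.2.4 places these sensitivity analyses at Week 12, so the one that matters for E-RS and SGRQ is not clearly planned.

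**The case against.** The strongest reply has four parts.

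1. Phone contact collects no variable in SAP Table 1, and exacerbations have no stated estimand. This is true of 7.2.3 alone. Sections 7.2.1 and 7.2.2 collect spirometry and SGRQ, and those are the data lost to the estimands. Exacerbation and SAE follow-up is a further gain, not an estimand conflict.
2. Protocol 9.4.4 promises only to use data that are collected, and it provides for study withdrawals through an exit visit and then imputation. This stands. A reader might infer that the Protocol contradicts its missing-data section. It does not; the fault is an avoidable limit on collection.
3. The exit visit and the letters reduce the loss. They do, but the letters leave the exit rule in force and the visit cannot show what happens afterwards.
4. The trial may be past the point of change, since SAP 17.5 describes early COVID-19 withdrawals in the past tense. If treatment has ended, only the analysis changes can still act.

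A reader might also attribute all missing Week 24 E-RS in these patients to this rule. The documents do not support that: 7.2.1 to 7.2.3 list neither E-RS nor the eDiary, so reduced follow-up would lose E-RS too. Keeping the diary going for all off-drug patients is a separate proposal. Nor does the amendment log's remark that sites manage COVID risk locally show that retention was judged safe; it explains only why testing became optional.

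**Conclusion.** The rule is real, current and out of step with the treatment-policy estimands. It stops spirometry, SGRQ, exacerbation and SAE follow-up that Section 7.2 could otherwise provide. Changing it is an inexpensive improvement.

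A reader might infer that the primary result is at risk. The numbers do not support that. At an assumed 5% exit rate, power is 89.1% if half leave before Week 12 and 88.3% if all do, and the bias bound of 3.0 mL takes every assumption at its worst. The effect on Week 24 SGRQ and on exacerbations cannot be sized from the documents; up to 16, 40 or 80 SGRQ values would rest on an exit visit or imputation at the assumed rates. Exacerbations are outside the test hierarchy. Every rate above, and the 0.70 rate ratio, is my assumption.

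**What to change.** **Protocol**

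1. Delete the study-withdrawal requirement for COVID-19 in 7.1, 7.1.6, 7.2 and 8.4.3.1, and keep the drug stop. Section 7.1.6 could read: patients with active COVID-19 discontinue blinded study medication and may remain in the study under Section 7.2, by phone while infectious, with clinic visits for spirometry and SGRQ once local rules allow.
2. State in 7.1 that early-termination assessments are also requested, when safe, from any of these patients who do leave.

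**SAP, including for patients already withdrawn**

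3. Correct the lead-in to 16.2.4 so that the planned tipping point runs at Week 24 for E-RS and SGRQ. Shifting COVID-19 withdrawals alone is not needed: at the same shift it is a weaker test than the planned one.
4. Add one sensitivity analysis of exacerbation rate and time to first event that imputes the time after COVID-19 withdrawal at the placebo rate.

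**Cost.** Items 1 and 2 need an amendment with ethics and, where applicable, regulatory approval (Protocol 11.2). With exits spread evenly over 24 weeks, the scheduled contacts still to come average 6/24 + 12/24 + 18/24 + 24/24 = 2.5 per patient to Week 24. Adding Weeks 30, 36, 42 and 48 gives 6.5 in the 48-week stratum. At the assumed 5%, split equally between strata, that is 20 × 2.5 + 20 × 6.5 = 180 contacts, some of them clinic visits; exits in Weeks 25–48 would add more. Off-drug values will slightly dilute the estimated effect, as the treatment-policy estimand intends. Items 3 and 4 need only a short SAP revision.

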7.1.7 Other Criteria

Other criteria that may or may not require permanent discontinuation of blinded study medication include but are not limited to adverse event, lack of efficacy, protocol deviation, non-compliance, study closed/terminated, investigator discretion or patient withdrawal of consent.

7.2 Study Participation After Discontinuation of Blinded Study Medication

Patients may permanently discontinue blinded study medication before the end of the study if they choose to or at the investigator's discretion.

Patients who permanently discontinue blinded study medication are not required to withdraw from the study unless they test positive for COVID-19 active disease. Patients who have permanently discontinued blinded study medication but do not test positive for COVID-19 active disease and have not withdrawn consent may continue in the study and complete all remaining protocol specified visits.

The Investigator must document the reason for discontinuation of blinded study medication in the eCRF.

Ideally, patients who have permanently discontinued blinded study medication will continue to attend scheduled clinic visits and complete important efficacy and safety assessments. However, if this is not possible then the investigator will encourage the patient to select one of the three options below to participate in as much of the study as they are willing (or able) to participate:

7.2.1 Reduced Assessments

The patient continues to follow the SoA (Section 1.3) and completes only the following assessments:

- Spirometry
- SGRQ
- COPD exacerbation
- AE
- Concomitant medication

7.2.2 Combination of Phone Contact and Reduced Assessments

The site contacts the patient by phone per the SoA (Section 1.3) to complete the following assessments:

- COPD exacerbation
- SAE
- Concomitant medication

In addition, the patient returns to the clinic at Week 24 (and Week 48 if in the Week 48 stratum) to complete the following assessments:

- Spirometry
- SGRQ
- COPD exacerbation
- SAE
- Concomitant medication

7.2.3 Phone Contact Only

The site contacts the patient by phone per the SoA (Section 1.3) to complete the following assessments:

- COPD exacerbation
- SAE
- Concomitant medication

7.3 Patient Discontinuation/Withdrawal from the Study

A patient may withdraw from the study at any time at his/her own request, may permanently discontinue blinded study medication but wish to remain in the study, or may be withdrawn from administration of blinded study medication or from all study participation at the discretion of the Investigator at any time for safety, behavioral, compliance, or administrative reasons. See the SoA (Section 1.3) for data to be collected at the time of study discontinuation and follow-up and for any further evaluations that need to be completed.

- If the patient withdraws consent for disclosure of future information, the Sponsor may retain and continue to use any data collected before such a withdrawal of consent.
- If a patient withdraws from the study, he/she may request destruction of any samples taken and not tested, and the Investigator must document this in the study center study records.

7.3.1 Early Termination/Withdrawal Procedures

If a patient is withdrawn prior to the Week 12 visit, every attempt should be made to have the patient complete the early termination/ withdrawal procedures in the SoA (Section 1.3) as soon as possible.

- If possible, patients should remain on blinded study medication and their maintenance LAMA or LABA medication and ICS (if applicable), follow the withholding procedures prior to Spirometry in Section 8.3.1.2, and should refrain from smoking or caffeinated beverages as recommended in Section 5.4.1.1.
- Patients unable to remain on blinded study medication and/or their maintenance LAMA or LABA medications and ICS (if applicable) should still complete the early termination/ withdrawal visit as soon as possible.

7.3.1.1 12-Hour Spirometry and 1.5 Hour ECG Procedures

For patients who are withdrawn prior to completing the Week 12 visit only, every attempt should be made to have the patient complete the 12-hour spirometry procedures and the ECG procedures at the early termination/withdrawal visit unless consent is withdrawn or the patient is being withdrawn for safety reasons precluding this assessment.

Patients who Continued Blinded Study Medication

Patients who have continued administration of their blinded study medication should complete the spirometry and ECG procedures as follows:

- Spirometry: Pre-dose and 0-12-hour post-dose assessments as per Section 1.4 and Section 8.3.1
- ECG: Pre-dose and 1.5-hour post-dose ECG procedures as per Section 8.4.2.

Patients who Discontinued Blinded Study Medication

Patients who have discontinued blinded study medication prior to the early termination/withdrawal visit may optionally complete spirometry and ECG assessments at the early termination visit if they have not already completed the Week 12 assessments. These patients will not be dosed with blinded study medication. If possible, patients should start spirometry between 6 am and 10am, withhold rescue medication and/or maintenance LAMA or LABA medications for the time period specified in Section 6.7.2, and refrain from caffeinated beverages and/or smoking for the time period specified in Section 5.4.1. The spirometry and ECG procedures should be completed as follows:

- Spirometry: Serial spirometry at 0-hour, 30 min, and 1, 2, 4, 6, 8, and 12 hours.
- ECG: 12-lead ECG at 0-hour and 1.5 hours.

Note: If a patient completed only one of the serial 12-hour spirometry or 1.5-hour ECG procedures at Week 12, they may optionally complete the other one (the one not completed at Week 12) at this visit.

7.3.1.2 Single 12-Lead ECG

Patients who early term/withdraw after Week 12 and are not completing either the pre-dose and 1.5-hour or the 0-hour and 1.5-hour ECG assessments described in Section 7.3.1.1 will complete a single 12-lead ECG as per Section 8.4.2.

7.4 Lost to Follow-up

A patient will be considered lost to follow-up if he or she repeatedly fails to return for scheduled visits and is unable to be contacted by the study center.

The following actions must be taken if a patient fails to return to the clinic for a required study visit:

- The study center must attempt to contact the patient and reschedule the missed visit as soon as possible and counsel the patient on the importance of maintaining the assigned visit schedule and ascertain whether the patient wishes to and/or should continue in the study.
- Before a patient is deemed lost to follow-up, the Investigator or designee must make every effort to regain contact with the patient (where possible, 3 telephone calls and, if necessary, a certified letter to the patient's last known mailing address or local equivalent methods). These contact attempts should be documented in the patient's medical record.
- Should the patient continue to be unreachable, he/she will be considered to have withdrawn from the study.

